### 4.3 Statistical Analysis Plan

Analyses will be conducted on data collected. While unlikely, data may not be missing at random (NMAR). [name], Project Biostatistician, will assign all lost responses to extreme category and perform multiple imputation procedures that can handle various amounts of missing data and use covariates and propensity scores.

The primary outcomes are detecting positive changes in knowledge acquisition and confidence, attitudes about bullying, self-efficacy regarding bullying, and intention to use of the STAC parent strategies. The secondary outcomes are program acceptability. A total of 20 parents within one school provides at least 80% power to detect a difference in baseline and immediate follow-up corresponding to a medium effect size (e.g., Cohen's  $d = .5$ ) with a 5% type I error probability. For this power analysis, pilot data from a sample of teachers were analyzed using measures similar to those proposed in this study. We will use three schools to ensure ecological validity and estimate the random effect for school for powering our future proposals involving multiple schools. We propose planning for 40 parents.

Descriptive statistics will be used to initially characterize the outcomes. We will use linear or generalized linear mixed model framework, with random effects of repeated observations on parents and parents nested within school.

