We will evaluate whether the STAC Parent Module increases knowledge and confidence, changes attitudes about bullying, and increases self-efficacy from baseline to immediate follow-up, as well as intention to use the STAC parent strategies at the immediate follow-up. We will also evaluate acceptability at the immediate follow-up. Means, SDs, and percentages will be used to describe the primary and secondary outcomes. To identify changes in outcomes, we will evaluate each outcome using analysis of variance in a linear or generalized linear mixed model framework, with random effects of repeated observations on parents and parents nested in school. We will address the appropriateness of the model for non-normal outcomes and apply the appropriate distribution as necessary, and we will assess models for the necessity of all random effects using Akaike information criterion (AICC). As the proposed project is intended to test feasibility and short-term outcomes to provide data for a larger multi-site study, we do not propose testing of moderators. However, we will examine demographic variables as a fixed effect whenever possible. Because our focus is on reception and usability, we will not perform a counterfactual analysis, but will have preliminary data to power for this in future proposals. Qualitative summary reports will also be prepared.

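### Section 4.3 lets AICc judge every random effect, including the parent effect that carries the pre-post pairing; the cost is small and mostly conservative, and one sentence removes it

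*Combined protocol and SAP*

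**What the plan says.** Section 4.3 states the model twice. Its first description is a linear or generalized linear mixed model "with random effects of repeated observations on parents and parents nested within school". The second, on the evaluation of change, says "we will evaluate each outcome using analysis of variance in a linear or generalized linear mixed model framework", again "with random effects of repeated observations on parents and parents nested in school". The selection rule follows: "we will assess models for the necessity of all random effects using Akaike information criterion".

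The only random effects named are those for parent and for school, so the rule covers both. No part of the document exempts the parent effect, confines AICc to school, or says what replaces the parent effect if it is judged unnecessary.

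Section 4.1.e gives a single-group design. In section 4.2, five of the six primary measures are taken at baseline and immediately after training: PAPPS, the NEA survey, the Parent Self-Efficacy Scale, the Attitudes about Bullying Questionnaire and the Student Social Behavior Questionnaire. Intention to use the strategies is taken only after training.

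**The concern.** With one group, the pre-post change is the only contrast for those five measures, and both scores come from the same parent. The dependence between them is a fact of the design, not a hypothesis for the data to accept or reject. If AICc removes the parent effect and nothing replaces it, 80 scores from 40 parents are analysed as if they came from 80 different parents.

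Two things are at stake. The standard error of the change no longer uses the pairing, and because the rule runs outcome by outcome, some primary measures could be analysed as paired and others as unpaired through sampling variation alone. For a pilot meant to inform later sample sizes, an outcome whose between-parent variance has been set to zero is also a poor planning input.

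**Working it through.** **Inputs.** From section 4.3: 40 parents planned, 5% type I error, d = 0.5. From section 4.2: two assessments for five primary measures. Assumed: normal scores with equal variances, complete pairs, no school variance, two-sided tests. Rho is not in the documents, so a range is used.

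**What the power statement implies about rho.** Section 4.3 says "A total of 20 parents within one school" "provides at least 80% power to detect a difference in baseline and immediate follow-up" at d = 0.5. If d is scaled by the SD of the change, a paired t-test with n = 20 has 56.5% power two-sided and 69.5% one-sided, so the stated 80% is not reproduced. If d is scaled by the raw SD, the standardised change is 0.5/√(2(1 − rho)), and 80% is reached at rho of about 0.71 (two-sided) or 0.62 (one-sided). The document gives neither the scaling nor rho.

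**When AICc drops the parent effect.** Let r be the estimated within-parent correlation, with the two variances pooled.

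- Likelihood gain from the parent intercept (REML, 39 df each for parent sums and differences): −39 ln(1 − r²) for r > 0, and zero for r ≤ 0.
- AICc penalty for one extra variance, N = 78: (4 + 12/75) − (2 + 4/76) = 4.160 − 2.053 = 2.107.
- The effect is dropped when r² < 1 − exp(−2.107/39) = 0.0526, that is r < 0.229. Full ML (penalty 2.218, 40 pairs) gives 0.232.

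**How often.** (1 + r)/(1 − r) is distributed as (1 + rho)/(1 − rho) times an F variable on 39 and 39 df. The drop probability is therefore P(F < 1.595 × (1 − rho)/(1 + rho)), where 1.595 = 1.229/0.771. At rho = 0.3 the bound is 1.595 × 0.7/1.3 = 0.859, which gives 32%. Simulation agrees throughout. The last column is 1 − (1 − p)⁵ for five measures treated as independent.

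| rho | parent effect dropped (p) | at least one of five |
|---|---|---|
| 0.2 | 57% | 99% |
| 0.3 | 32% | 85% |
| 0.4 | 12% | 47% |
| 0.5 | 2.5% | 12% |
| 0.6 | 0.3% | 1% |
| 0.7 | 0.01% | under 0.1% |

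**Size of the error when dropped.** In the same data, unpaired SE / paired SE = 1/√(1 − r). Since r < 0.229, the ratio cannot exceed 1/√0.771 = 1.139. Its mean among dropped cases is 1.054, 1.073, 1.089 and 1.098 at rho 0.2, 0.3, 0.4 and 0.5. Type I error among dropped cases is about 3.0% at rho 0.2 and 2.4% at rho 0.3, so those tests are conservative.

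**Effect on the whole procedure** (d = 0.5 on the raw SD, simulated):

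| rho | power, pairing always kept | power, AICc selection |
|---|---|---|
| 0.2 | 68.3% | 66.7% |
| 0.3 | 74.4% | 73.0% |
| 0.4 | 80.3% | 79.7% |
| 0.5 | 87.2% | 87.1% |
| 0.7 | 97.8% | 97.8% |

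The largest loss is 68.3 − 66.7 = 1.6 points. Overall type I error under selection lies between 4.6% and 5.4% for rho from 0 to 0.7.

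**The case against.** The best defence is that the rule largely limits its own damage. AICc drops the parent effect only when the observed correlation is below about 0.23, where pairing gains little. Hence the near-nominal overall type I error and the small power loss. This stands, and it is why the point is minor.

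Second, rho may be high. The same questionnaires are completed twice in one evening around a 50-minute session, and under the raw-SD reading the power statement needs rho of about 0.6 to 0.7, where dropping almost never happens. That is fair, but the plan does not state rho, and it would have to be high for every measure for the rule to be harmless.

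Third, the plan speaks of assessing necessity and does not say that a term will be deleted. An analyst could compute AICc and still keep the design structure. That is true, though removal is the usual consequence of failing such a check, and the text offers no other.

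Three stronger readings are tempting and are not supported:

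- **The error bars could be too narrow.** At rho 0.2, the unpaired SE is below the paired SE in about 18% of dropped cases. These are datasets with a negative sample correlation, where chance inflates the paired estimate. Against the true SE, the unpaired one there averages about 8% too wide, and type I error is 3.4%.
- **All primary outcomes are exposed.** Intention to use has one measurement and no pairing to lose.
- **Dropping the school effect does the same harm.** With complete data, a school intercept does not enter the standard error of the within-parent change.

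**Conclusion.** The concern holds as a minor specification gap. Section 4.3 exposes a feature fixed by design to a data-driven rule, outcome by outcome, and nothing protects it. Whether this matters depends on an unstated correlation: losing the pairing in at least one of the five measures is likely at rho of 0.3 or below, about even at 0.4, and negligible from 0.6 upwards. Where it happens, the interval for the change is usually 5-10% too wide, and never more than 14% wider than the paired one.

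A reader might infer that the primary tests are invalid or that false positives are inflated. The calculations do not show that: overall type I error stays near 5%, and the tests affected are conservative for positive rho.

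The figures assume 40 complete pairs, normal scores, equal variances and no school variance. The generalized linear case was not simulated, and the five-measure probabilities treat the measures as independent.

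**What to change.** Add one sentence to section 4.3, for example: *For outcomes measured at both assessments, the correlation between a parent's two scores is always modelled and is not subject to selection; AICc is used only for terms whose removal leaves this pairing intact.*

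An unrestricted within-parent residual covariance is the better form for continuous scores. It is not interchangeable with a parent random intercept: when the sample correlation is negative, the intercept variance is estimated as zero and the analysis falls back to the unpaired one, whereas a residual covariance can be negative. For outcomes that need a generalized linear model, the same sentence should say which within-parent term is kept.

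The school term may remain under AICc as far as this point goes. But section 4.3 also says "We will use three schools to ensure ecological validity and estimate the random effect for school" for later proposals, so that variance should be reported whatever AICc indicates.

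The change needs no data. Always keeping the pairing matches or improves power from rho 0.1 upwards. Only at rho 0 is it lower (58.7% against 60.6%), and there the selection rule's own type I error is slightly above 5% (5.3%).
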